developed for the POWER trial⁷⁸ and has been adapted for PROPEL. The questionnaire assesses the primary care provider’s demographic information (age, race, training, specialty, years in practice, weight, and height), and knowledge about weight management practices (calculation of BMI, weight loss counseling and referral, etc.). The survey will be programmed into the REDCap system, which will also send each participating provider an email requesting that they complete the web-based survey. If a provider has not completed the survey within 2 days, the REDCap system will send 2 additional reminder emails 2 days apart. All contact information and survey responses will be kept private.

Concomitant Medications Form

Patients will be asked to bring their medications to the screening visit and all subsequent assessment visits. A concomitant medications form (see Appendix A), adapted from prior trials, will be completed by a member of the research team at each visit to track changes in the patient’s medications throughout the trial.

Adverse Events

A surveillance form, adapted from prior trials, will be used to screen for adverse events and serious adverse events (SAEs) at each assessment visit (see Appendix A). The following events will not be recorded as they are viewed as expected or unrelated to the study (unless the event meets the definition of an SAE): constipation, joint/muscle pain, and fall-related injuries (other than those related to a secondary condition such as vertigo). All SAEs will be recorded and reported. Serious, unexpected AEs that are related or are possibly related to the study will be reported to the IRB in accordance with requirements.

Table 2. Data measurement and collection schedule for patient data.

Measurement	SV	BV	V6	V12	V18	V24
Anthropometry						
Weight	X	X	X	X	X	X
Height	X	X				
Waist Circumference		X	X	X	X	X
Risk Factors						
Blood Pressure and Pulse		X	X	X	X	X
Fasting Finger-stick Blood Sample		X		X		X
Questionnaires						
Baseline Demographics and Health History	X					
Change in Health History			X	X	X	X
REALM-SF	X					
Food Security		X		X		X
Eating Inventory		X	X	X		X
PROMIS-29		X	X	X		X
Impact of Weight on Quality of Life – Lite		X	X	X		X
IPAQ-SF		X	X	X		X
Dietary Intake Questionnaire		X	X	X		X
Concomitant Medications		X	X	X	X	X
Adverse Event Form			X	X	X	X
Patient-Provider Survey		X				X

Intervention Satisfaction Survey*			X			X
-----------------------------------	--	--	---	--	--	---

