- e) Increased physical activity. Patients in the intervention arm will be counseled to increase physical activity to levels that are consistent with the recommendations for US adults (30 minutes of moderate intensity activity per day). There is the possibility of adverse events such as minor musculoskeletal problems, but risk is minimized by excluding potential participants with contraindications to exercise. Considering these types of events are expected in this trial they will not be recorded or reported unless they meet the definition of a Serious Adverse Event. Patients with diabetes or prior CVD must have physician approval to begin exercise.
- f) Hypoglycemia during weight loss for patients on insulin and insulin secretagogues. To minimize hypoglycemia with weight loss in persons with type 2 diabetes, we will ask patients to monitor their blood sugar at least twice a day, once in the morning before breakfast and once in the evening before dinner.
- g) Gall bladder disease with weight loss. All physicians will be educated on the health risks associated with weight loss. With the slow weight loss we anticipate, we do not expect gall bladder disease exacerbation and will not give patient prophylaxis with ursodiol or fat bolus; for patients with symptoms of gall bladder disease, we will advise appropriate evaluation and treatment.

Adequacy of Protection against Risks

Recruitment and Informed Consent

The patients are volunteers that will be recruited through the primary care clinics. Potential subjects will then be screened in person to determine that they meet the initial recruitment criteria (such as age and BMI) and have no obvious contraindications to participating in the study. Screening of study participants will be conducted by a trained recruiter following a written manual of procedures. In a one-on-one or group consenting session, the potential participant(s) will be informed of the nature and requirements of the study, either via face-to-face interview or informed consent presentation. All patients will be given time to read the consent form and ask questions one-on-one with PROPEL staff. To continue, the participant must read and sign an informed consent to participate in further assessment and treatment.

Protection against Risks

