A. Data Quality and Management – A Data and Safety Monitoring Board (DSMB) will be convened and will meet regularly throughout the study period. The DSMB will meet twice per year throughout the trial, and will be convened for a first meeting prior to recruitment of patients. A minimum of 1 meeting each year will be conducted in person, and the second meeting may be conducted via conference call. Prior to the start of recruitment the DSMB will give formal approval of the study protocol and informed consent.

Size and Composition of DSMB: The DSMB will consist of 4 members both internal and external to the Pennington Biomedical Research Center. The planned composition is as follows: biostatistician (1), exercise physiologist or dietician (1), clinician (1) and layperson (1).

Major Responsibilities of DSMB Members:

1. Sign and abide by a statement of confidentiality
2. Disclose any actual or potential conflicts of interest
3. Create a charter to define its function, signed by all members
4. Be familiar with the research protocol and plans for safety monitoring
5. Oversee safety of participants, which will include review of interim/cumulative data for evidence of study-related adverse events (including serious adverse events)
6. Review data quality, completeness, and timeliness (including recruitment)
7. Review adherence to the protocol
8. Review factors that might affect the study outcome or compromise the confidentiality of the trial data (such as protocol violations, unmasking, etc.)
9. Review reports of related studies, as appropriate
10. Review major proposed protocol modifications

Reports: Following each meeting, the DSMB will provide written documentation regarding findings for the study as a whole and any relevant recommendations related to continuing, changing, or terminating the study. All DSMB recommendations will be submitted to the Principal Investigator and/or his designee, with a copy provided to the Pennington Biomedical Research Center IRB and PCORI Project Officer or designee.

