D. Stopping Rules - This study will be stopped prior to its completion if: (1) adverse effects that significantly impact the risk-benefit ratio have been observed; (2) study recruitment or retention becomes futile; (3) any new information becomes available during the trial that necessitates stopping the trial; and (5) other situations occur that might warrant stopping the trial. Because one of the most likely reasons for stopping the trial is the inability to recruit the study sample, the PI will include an assessment of recruitment futility in the annual progress report to PCORI and will consult with a biostatistician if necessary to assess the impact of significant data loss due to problems in recruitment, retention or data collection.

E. Justification of Sample Size - The sample size calculations for PROPEL were based on LOSS, a pragmatic clinical trial conducted by Pennington Biomedical in eight primary care clinics across the state of Louisiana comparing intensive medical intervention for obesity versus usual care.⁴ According to the *2013 AHA/ACC/TOS Obesity Guidelines*, as little as 3-5% weight loss is likely to result in clinically meaningful health outcomes.²⁹ The calculations assume that

the study will be powered to detect a mean weight loss in the intervention arm of 3.5% at 2 y, relative to usual care, in race- and sex-specific subgroups. We are targeting a mean weight loss of >5% which we anticipate to be 3.5% more than usual care. Both the total and relative weight loss meet currently accepted levels of clinical significance.

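### Non-serious joint or muscle pain, constipation and fall injuries not tied to a secondary condition go unrecorded in both arms, so their rates cannot be compared

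*Combined protocol and SAP*

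**What the plan says.** Section 11 (Adverse Events) sets up a surveillance form at each assessment visit. Table 2 places it at months 6, 12, 18 and 24, with no form at baseline and no restriction by arm. The section then states: "The following events will not be recorded as they are viewed as expected or unrelated to the study". Two exceptions follow.

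- **Serious cases.** The rule applies "unless the event meets the definition of an SAE): constipation, joint/muscle pain, and fall-related injuries". The section adds that "All SAEs will be recorded and reported".
- **Some falls.** The excluded falls are "fall-related injuries (other than those related to a secondary condition such as vertigo", so falls with such a cause are recorded.

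Section 14 returns to the subject twice in the same terms, under Potential Risks (item e) and in the Data and Safety Monitoring Plan, part IV.D (item e). Both deal with the increased activity asked of intervention patients and say: "There is the possibility of adverse events such as minor musculoskeletal problems". Both then say: "Considering these types of events are expected in this trial they will not be recorded or reported unless they meet the definition of a Serious" (the sentence closes by naming an SAE).

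Part IV.A of the monitoring plan defines an adverse event broadly and makes no exemption for expected events. Part V.A gives the DSMB the task of "review of interim/cumulative data for evidence of study-related adverse events". Stopping rule 1 in part V.D applies when "adverse effects that significantly impact the risk-benefit ratio have been observed". Section 16 describes no between-arm comparison of adverse events.

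**The concern.** Whether an event is expected bears on how fast and in what detail it is reported. It does not settle whether the event should be counted. If the activity programme is expected to cause musculoskeletal problems, the useful quantity is the excess over usual care, and that needs counts from both arms.

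The stated reason also fits poorly with the rest of the document. Section 11 treats the listed events as expected or unrelated, while Section 14 attributes one of them to the intervention. The intervention goal in Section 10 is at least 175 minutes of moderate-to-vigorous activity per week, in patients with a BMI of 30 to 50. A difference between arms in musculoskeletal complaints is therefore plausible on the protocol's own account.

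At stake is the non-serious part of the safety comparison. The final report could not say how much more often, if at all, intervention patients had these complaints, and the DSMB would not see them accumulate.

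**Working it through.** **Step 1: what is lost and what remains.** This is mainly a check of the text.

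| Event | Non-serious | Serious | Other source |
|---|---|---|---|
| Joint or muscle pain | not recorded | recorded | PROMIS-29 pain interference and pain intensity at baseline, 6, 12 and 24 months |
| Constipation | not recorded | recorded | none described |
| Fall injury, no secondary condition | not recorded | recorded | none described |
| Fall injury from a secondary condition such as vertigo | recorded | recorded | not applicable |

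The rule covers both arms, so it does not bias a comparison. It removes the comparison.

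**Step 2: consistency with the monitoring plan.** Part IV.C has the Medical Monitoring Team confirm relatedness, and part IV.D has it decide expectedness. The Section 11 rule settles both in advance for whole event types. Section 14 speaks of minor problems, but Section 11 sets no severity limit. Part IV.B grades severity separately from seriousness, so an event graded severe but not serious would also go unrecorded if it is on the list.

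**Step 3: what recording could show.** The plan has no adverse-event rate or precision figure to reproduce, so the following is illustrative only.

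Inputs from the documents: 425 patients per arm and 47 per clinic (Section 15), hence 9 clinics per arm if the 18 are split evenly; 30% attrition; 92 per arm under patient randomization against 134 under clinic randomization.

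Assumed inputs: cumulative rates of 10% (usual care) and 16% (intervention), and an ICC of 0 to 0.033.

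The upper ICC comes from the plan's own inflation for weight change:
- design effect = 134/92 = 1.457
- patients per clinic = 134/9 = 14.9
- ICC = (1.457 − 1)/(14.9 − 1) = 0.033 (0.0329 before rounding)

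Applying this to adverse events is a further assumption.

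Half-width without clustering, 425 per arm: 1.96 × √(0.10 × 0.90/425 + 0.16 × 0.84/425) = 1.96 × √(0.2244/425) = 0.045.

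With clustering, multiply by √(1 + (m − 1) × ICC). Before attrition m = 47. After 30% attrition, n = 425 × 0.70 ≈ 298 per arm and m = 298/9 ≈ 33.1, and the unclustered half-width is 1.96 × √(0.2244/298) = 0.054.

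| Per arm | ICC | Design effect | 95% half-width (points) |
|---|---|---|---|
| 425 | 0 | 1 | 4.5 |
| 425 | 0.01 | 1 + 46 × 0.01 = 1.46 | 5.4 |
| 425 | 0.0329 | 1 + 46 × 0.0329 = 2.51 | 7.1 |
| 298 | 0 | 1 | 5.4 |
| 298 | 0.01 | 1 + 32.1 × 0.01 = 1.32 | 6.2 |
| 298 | 0.0329 | 1 + 32.1 × 0.0329 = 2.06 | 7.7 |

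The assumed 6-point difference would be separable from zero in the more favourable rows only. As planned, there is no estimate at all.

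**The case against.** The strongest reply is that the rule is narrow, disclosed and deliberate. The trial is described as carrying no major risk, and the DSMB must approve the protocol before recruitment. Serious cases are captured in both arms. PROMIS-29 supports a baseline-adjusted comparison of pain. The change-in-health questionnaire, medications form and chart review may add something, though the content of those forms is not shown. Minor symptoms reported by patients who know their assignment (Section 9) are soft data in any case.

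Much of this stands, and it rules out several stronger readings that a reader might infer.

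- **That a fracture treated without admission must leave no record.** The SAE definition in part IV.A includes significant disability and medically important events, so admission is not required. Part IV.E has clinics report events of uncertain seriousness within 24 hours. Such a fracture could be captured.
- **That the DSMB and stopping rule 1 are blind to these harms.** They see the serious cases and the recorded falls. They miss the non-serious remainder.
- **That the main harms of the programme are unobserved, so benefit and risk cannot be weighed.** Only musculoskeletal problems are tied to the programme. The documents do not name constipation as a risk of the diet or falls as a risk of the activity. Hypoglycemia and gall bladder disease, also named as risks, are not on the excluded list.

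The reply does not restore the missing rates. PROMIS-29 yields scores rather than event counts, does not give the site or cause of pain, and is not collected at month 18. A mean pain score could also improve with weight loss while some patients are injured. It says nothing about constipation or falls. The chart review is retrospective, and no abstraction of adverse events is described.

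**Conclusion.** The point holds for non-serious events. Non-serious joint or muscle pain, constipation and fall injuries without a secondary cause are not recorded in either arm. Their rates, including those of the musculoskeletal events that the protocol itself expects from the activity programme, cannot be compared between arms or reviewed by the DSMB. SAEs and PROMIS-29 pain scores are the only described sources that can be relied on for these complaints.

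No effect size can be read from the documents. Under the assumed 10% and 16%, recording would give a 95% half-width of about 4.5 points ignoring clustering, 5.4 to 7.1 points at an ICC of 0.01 to 0.033, and about 6.2 to 7.7 points at the same ICCs after 30% attrition. Recording would therefore give a usable but not sharp estimate.

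The primary outcome and its analysis are unaffected. This is a cheap improvement to the safety data, not a flaw that threatens the trial's main conclusion.

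**What to change.** Replace the rule against recording with yes/no items on the existing surveillance form at months 6, 12, 18 and 24 in both arms:

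1. joint or muscle pain that needed care or limited activity;
2. constipation;
3. fall injury.

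Ask the same items once at baseline, where Table 2 currently has no adverse-event form, so that new complaints can be separated from existing ones. Require no narrative and no expedited reporting for non-serious cases. Bring both Section 14 statements into line. Tabulate the items by arm for the DSMB and the final report, with intervals that account for clustering by clinic.

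The cost is about a minute per visit and more non-serious events to tabulate. Patients know their assignment, so self-report may differ by arm. Identical questions on an identical schedule limit this but do not remove it, and the report should say so.

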Finger-stick blood samples will be used to measure fasting levels of lipids (total cholesterol, HDL cholesterol, LDL cholesterol, triglycerides) and glucose using a validated Cholestech LDX point-of-care device^{62,63} at baseline, month 12 and month 24 visits. The patients will be asked to arrive at the clinic after fasting from 10 pm on the prior evening. The LDX is a small, portable analyzer that requires only a single drop of blood from a finger stick and eliminates the anxiety of a venipuncture. The research assistant will clean the patient's fingertip with an alcohol wipe and obtain a drop of blood using a lancet. The blood is collected via capillary tube and transferred to the LDX cassette. The results will available in less than five minutes, and LDX printout will be transferred to the PROPEL Physical Measurement Form (see Appendix A) and data-entered by the research staff. The LDX will print a second results label which will be attached to the Cholestech Patient Results Label Log.

Questionnaires

All questionnaires will be completed in paper form by patients, and subsequently data-entered by research staff. Patients with low health literacy, as established by the REALM SF (described below) will complete the questionnaires using a semi-structured interview format with the help of research staff.

Baseline Demographic and Health History Questionnaire

A self-report demographic and health history questionnaire (see Appendix A) asks the patients about their age, sex, race/ethnicity, use of tobacco and alcohol, health insurance status, post-menopausal status, income and employment, education level, and history of chronic diseases. Further, the questionnaire collects information on their physical home address and nearest cross-street for the purpose of built-environment analyses. This questionnaire will be administered at SV.

Change in Health History Questionnaire

A self-report questionnaire captures changes in health outcomes that have occurred across the 2 years of the intervention (see Appendix A). This questionnaire is administered at the 6, 12, 18 and 24 month assessment visits.

REALM-SF

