The DSMB will monitor and review recruitment, adverse events, data quality, outcome data, and overall awardee performance. The PI and Project Manager will regularly review all data collection forms and source documents on an ongoing basis for data completeness, accuracy, and compliance with the protocol and Standard Operating Procedures (SOPs) of PBRC. A statement reflecting the results of the review and describing any protocol deviations will be sent to the PBRC IRB in an annual report (non-competing continuation).

B. Subject Accrual and Compliance - Review of subject accrual, adherence to inclusion / exclusion criteria, and rates of study completion will occur quarterly. These data will be reviewed by the study PI and Medical Monitoring Team and presented to the DSMB.

C. Out of Range Data – Laboratory and physical measurement reports will be reviewed weekly by the Medical Monitoring Team for the study. Out-of-range values for clinical chemistry and blood pressure will be reported to the patient as soon as possible so that they can follow up with their PCP. See Table 3 for Alert and Emergency values and actions.

Table 3. Alert and Emergency Values and Actions

Measure	Alert Value	Notify Participant	Notify PCP
Blood Pressure	Systolic ≥ 150 mmHg or Diastolic ≥ 100 mmHg	Within 1 week or sooner as indicated by exact value and judgment of Medical Monitor	Instruct the participant to notify their PCP within 1 week or sooner as indicated by exact value and judgment of Medical Monitor
Blood Glucose	≥ 200 mg/dl or ≤ 400 mg/dl	Within 1 week or sooner as indicated by exact value and judgment of Medical Monitor	Instruct the participant to notify their PCP within 1 week or sooner as indicated by exact value and judgment of Medical Monitor
Triglycerides	>650 mg/dl	Within 1 week or sooner as indicated by exact value and judgment of Medical Monitor	Instruct the participant to notify their PCP within 1 week or sooner as indicated by exact value and judgment of Medical Monitor

Measure	Emergency Value	Notify Participant
Blood Pressure	Systolic ≥ 170 mmHg or Diastolic ≥ 110 mmHg	Instruct the participant to take their medications if they have not already and immediately walk with them to find clinic personnel who can evaluate them for possible additional treatment.
Blood Glucose	<50 mg/dl or >400 mg/dl	Immediately walk with the participant to find clinic personnel who can evaluate them for possible additional treatment.

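### The blood glucose alert value in Table 3 is met by every possible reading; "or" should almost certainly be "and"

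*Combined protocol and SAP*

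**What the plan says.** Section 14 (Safety and Data Monitoring), item V.C, Out of Range Data, states the purpose: "Out-of-range values for clinical chemistry and blood pressure will be reported to the patient as soon as possible". It then makes the table the working definition: "See Table 3 for Alert and Emergency values and actions".

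Table 3 has two tiers for glucose:

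- Alert: "≥ 200 mg/dl or ≤ 400 mg/dl". The participant is to be told "Within 1 week or sooner as indicated by exact value and judgment of Medical Monitor" and asked to inform their primary care provider on the same timescale.
- Emergency: "<50 mg/dl or >400 mg/dl". Staff are to take the participant straight to clinic personnel for evaluation.

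Section 11 (Fasting Finger-stick Blood Sample) says that glucose is measured on a "point-of-care device^{62,63} at baseline, month 12 and month 24 visits", and that the samples are fasting: "The patients will be asked to arrive at the clinic after fasting from 10 pm on the prior evening". The protocol gives no other glucose alert limit.

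**The concern.** An alert limit has to divide readings into those that need action and those that do not. This one joins two overlapping half-lines of the same measurement with *or*, so it excludes nothing. Taken literally, every participant with an ordinary fasting glucose must be notified and told to contact their provider, and staff who do not do so depart from the protocol.

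In practice staff would probably infer a range for themselves. That is a weak basis for a safety threshold here. The trial has 18 clinics that Section 12 describes as remote and hard to visit, it admits patients with controlled diabetes (Section 7), and it names hypoglycemia as a risk for those on insulin or secretagogues (Section 14). The written limit should not depend on each reader guessing what was meant.

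**Working it through.** **Inputs.** The alert and emergency conditions come from Table 3. The measurement schedule comes from Section 11: baseline, month 12 and month 24. The maximum enrollment of 850 and the planned 30% attrition come from Section 15.

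**Step 1: the rule as written.** The alert set is {g ≥ 200} ∪ {g ≤ 400}. A reading escapes it only if g < 200 and g > 400 together, which is impossible. The union is therefore the whole line.

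**Step 2: spot values.**

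| Glucose (mg/dl) | Alert as written | Alert with *and* | Emergency |
|---|---|---|---|
| 40 | yes | no | yes |
| 50 | yes | no | no |
| 90 | yes | no | no |
| 199 | yes | no | no |
| 200 | yes | yes | no |
| 400 | yes | yes | no |
| 401 | yes | no | yes |

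**Step 3: check on a grid.** Over the integers 0–999 mg/dl, used only to test the logic and not as a distribution of patients:

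- Alert as written: 1,000 of 1,000.
- Alert with *and*: 200–400, which is 400 − 200 + 1 = 201 values.
- Emergency: 0–49 and 401–999, which is 50 + 599 = 649 values.
- Neither tier, once the alert row is corrected: 50–199, which is 150 values.
- Corrected alert and emergency together: 0 values shared.
- Total: 201 + 649 + 150 = 1,000.

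The band wrongly flagged by the present wording is therefore 50–199 mg/dl. The written alert also covers all 649 emergency values, so it does not distinguish the two tiers either.

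**Step 4: is *or* used loosely throughout Table 3?** No. In the blood pressure rows it joins two different measures, systolic and diastolic. In the glucose emergency row it joins opposite tails. Both uses are sound. Only the glucose alert row is always true.

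**Step 5: how many samples the rule covers.**

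- No attrition: 850 × 3 = 2,550.
- 30% lost, all after month 12: 850 + 850 + 595 = 2,295, where 850 × 0.7 = 595.
- 30% already lost by month 12: 850 + 595 + 595 = 2,040.

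The protocol does not give the timing of attrition, so the last two figures show a range under assumed timing. All three count samples subject to the rule. The number that would fall in 50–199 mg/dl cannot be derived, because the protocol gives no glucose distribution.

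**The case against.** The best case on the other side accepts the error and disputes its weight and its repair.

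*Weight.* The dangerous readings are caught by an emergency row that works. The Medical Monitoring Team reviews laboratory reports weekly, and the timing of an alert notice already depends on the medical monitor's judgment. The likely result of literal use is unnecessary notices, not missed ones. The manual of procedures and the measurement forms, which are not reproduced in the protocol text, may also guide staff. All of this stands and limits the consequence. It does not make the written criterion correct, and nothing in the protocol itself corrects it.

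*Repair.* The 200–400 band is an inference. The blood pressure alert has no upper cap although its emergency tier starts higher, so an uncapped alert at 200 mg/dl and above would also fit the table's style. Alternatively, the author may have meant a high limit or a low limit, as in the emergency row, and mistyped the second number. These alternatives are possible. The coincidence of 400 with the emergency cut-off makes the band the most natural reading, but the documents do not settle it, so the medical monitor has to confirm.

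**Conclusion.** The concern holds. As written, the glucose alert condition is true of every reading and cannot identify out-of-range values; readings of 50–199 mg/dl are flagged without reason. The logic needs no assumption beyond the text of Table 3.

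The consequence is modest. The fault runs only towards over-notification and is confined to the alert tier. It has no bearing on type I error, power or the efficacy analysis. It should be corrected because it is a decision rule that the safety plan relies on, but it does not threaten the trial. What remains uncertain is the intended range: 200–400 mg/dl is probable, not proven.

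**What to change.** In Table 3, change the blood glucose alert value to: ≥ 200 mg/dl *and* ≤ 400 mg/dl. Ask the medical monitor to confirm two things:

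1. That 200–400 mg/dl is the intended band, rather than an uncapped limit at 200 mg/dl.
2. Whether a low alert limit at or just above 50 mg/dl was also wanted. The corrected row has no alert tier above the <50 mg/dl emergency limit.

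The cost is one word in the table and one confirmation. If the manual of procedures or the measurement form repeats the threshold, the same correction should be made there.
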